The primary study (Visits 2-5) is divided into three phases, with each lasting about 4 weeks (**Figure 1**). Prior to returning for Visit 2, participants will record their 24-hr dietary intake over three days using the Automated Self-administered 24-hour (ASA24) dietary assessment tool. At Visit 2, participants will return their stool sample, and baseline data collection will be performed that includes anthropometrics, questionnaires, any updates to the medical history questionnaire and a blood draw. Participants will then be randomly assigned to the AB or BA intervention sequence using a computer-generated list of random numbers. Instructions will be provided on the run-in protocol and incorporating dried plum into the diet (50 g/day or 5-6 dried plums per day) or not based on their sequence. Study personnel will provide the dried plums in snack packs at no cost. Note the snack packs will be provided by the California Prune Board. At Visit 3, participants will complete the data and sample collection as described for Visit 2 and then begin the washout period. Visit 4 will be scheduled following the washout period and the same procedures described in Visit 3 will be repeated with crossover to the second intervention. At Visit 5 (final visit), participants will complete the data and sample collection. At Visits 3 or 5, any remaining dried plums will be returned. All procedures will strictly adhere to the guidelines set forth by the Indiana University School of Medicine Institutional Review Board. The study will be registered with ClinicalTrials.gov.

**Figure 1. Overview of Experimental Design.** Postmenopausal women ( $n >= 30$ ) will be randomized to one of two treatment sequences (AB or BA) and complete 5 study visits (*details below*). Each treatment period (Phase 1 & 3) will consist of an approximately 1-wk run-in followed by 4 wks of treatment with a 3-4 wk washout in between.

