## 8.0 STUDY PROCEDURES:

**Health and Medical History.** Relevant medical history will be obtained at Visit 1 by the Study Coordinator. The information collected will include a brief medical history, questions related to health behaviors, reproductive history, bone health history (i.e., incidence of previous fractures), prior oral contraceptive and hormone replacement use, as well as the use of other medications and supplements (*See Medical History Form*). The health and medical history will be updated at each subsequent visit to account for any changes occurring over the course of the study. Any concerns raised will be brought to the attention of the CRC staff physician for recommendations.

**FIT Core.** At Visit 1, participants will complete assessments at the FIT Core (IRB study #1707550885). This will include but is not limited to providing additional information related to their medical history, medications, and body composition (height, weight). They will be asked to answer questionnaires regarding their physical function and physical activity and will undergo a DEXA or bone density test. Participants will also be asked to complete a battery of tests related to their physical capacity, including hand grip strength, repeated chair stands, gait speed, timed up-and-go, a six-minute walk test, and a balance assessment.

**Blood Sample Collection.** Participants will provide fasting blood specimens, collected between 7:30-10:00 AM at baseline and final time points in each period (Visit 2-5). Whole blood (~21 mL) will be collected in CPT tubes (BD Biosciences) for FACS analyses and *ex vivo* experiments with PBMCs to characterize Th17 and Treg abundance and function. One additional tube (~5 mL) will be collected and processed for serum, and stored at -80°C for metabolomics, cytokines, 25(OH)D and bone biomarkers.

**Fecal Sample.** Participants will be asked to collect 2 stool samples prior to each visit (Visits 2-5) using a sample collection kit (DNA GeneTek). They will be also asked to rate their stool consistency using the Bristol Stool Scale, as well as ease of passage using a 5-point Likert scale (1 = very easy, 2 = easy, 3 = neither easy nor difficult, 4 = difficult, 5 = very difficult) as we have previously reported [49].

**Anthropometric Measurements.** Height and weight will be assessed at each visit and body mass index (BMI kg/m^2) calculated.

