## **11.0 STATISTICAL CONSIDERATION:**

**Power Calculation.** Although we anticipate a low attrition rate due to the utilization of an effective run-in period as previously described [35], we conservatively incorporated a 10% attrition rate in our power calculation. Our sample size has 80% power to detect an effect size of 0.8 standardized mean difference in the immune response between the treatment with dried plum and control (i.e., no dried plum). Based on a previous study of the anti-inflammatory effect of dried plum in a similar population of postmenopausal women consuming 50 g/d [51], an effect size of approximately 1.5 SD was observed for serum IL-6 when comparing the dried plum group to the control group. Thus, our study sample size (n=30) provides adequate power to detect expected treatment effects. Power estimation was conducted our by biostatistician and co-PD, *[name]*, using PASS v19.

**Statistical Analyses.** De-identified data will be analyzed using PC SAS version 9.4 and SAS PROC MIXED, GLIMMIX, and GLM. Descriptive statistics will be calculated for all variables and will include means, SD, medians, and minima/maxima. Distributions of outcome variables will be examined graphically using histograms and box plots for symmetry and for outliers. Logarithmic transformation will be applied to non-normally distributed data. For our primary outcomes, we will use linear mixed effects models to determine if the level of serum IL-6 and T cells (i.e., Th17) at the end of each period is significantly different for dried plum compared to the control. Baseline measures, treatment and period indicators,

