vitamin D (i.e., serum 25-OH D), and important demographic characteristics (e.g., age, BMI, years post menopause) will be included as fixed effects. Random participant effects will be included to accommodate the correlations among repeated measures. We will test for a carry-over effects, but we assume there will be no effect after adjusting for baseline and period effects. We will perform a per protocol analysis on the primary outcomes, which includes only those who completed the intervention and who were compliant ( $\geq 85\%$ ) with the study protocol. Hypothesis tests for the treatment effect will be carried out following standard procedures for mixed-effects models [52]. Similarly, for secondary outcome measures (i.e., gut microbiota, metabolites, and bone resorption markers), we will use separate mixed effects models, adjusting for baseline, period, and demographic covariates. Categorical variables will be assessed using the generalized linear mixed-effects models. Importantly, to gain a better understanding of the gut-bone axis response, we will also integrate the immunologic outcomes (i.e., T cell), metabolomics, microbial taxa and bone biomarker data. These analyses will include regression analyses to correlate key outcomes. In addition, we will explore if dried plum consumption modulates the immune response via alterations in metabolite and microbiota profiles by conducting exploratory mediation analysis. For all statistical analyses, alpha will be set at 0.05.

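### If each period's baseline enters the primary model as one covariate beside the random participant effect, the treatment contrast can lose precision; separate woman-mean and period-deviation terms avoid this at little cost

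*Protocol*

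**What the plan says.** Section 11.0 (Statistical Analyses) gives the primary model. The response is the level of serum IL-6 or Th17 at the end of each period. The fixed effects begin with "Baseline measures, treatment and period indicators" and go on to vitamin D and demographic characteristics. The within-woman correlation is handled by one further term: "Random participant effects will be included to accommodate the correlations among repeated measures".

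Section 8.0 (Blood Sample Collection) has fasting blood drawn "at baseline and final time points in each period (Visit 2-5"), so each woman has two baselines (Visits 2 and 4) and two end-of-period values (Visits 3 and 5). Section 11.0 also discounts carry-over on the ground that baseline and period are adjusted for. Visit 2 precedes all treatment, so only a baseline that includes Visit 4 could serve that purpose.

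Section 11.0 does not say in so many words which baseline is meant, or whether it enters as one term or two. It states no correlation between visits.

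**The concern.** In a two-period crossover the treatment effect is estimated from differences within woman. A baseline that changes from period to period carries two relations. One is between women: a woman with generally high Th17 has high values at every visit. The other is within woman: a baseline above her own average may or may not predict an end-of-period value above her own average. For a stable marker the first relation is strong and the second can be close to nil.

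A single covariate beside a random intercept gets one slope for both, and the strong between-woman relation pulls that slope upward. The within-woman contrast is then corrected by too large a multiple of the Visit 2 to Visit 4 difference, and the noise in that difference enters the treatment estimate. What is at stake is the precision that the crossover design was chosen to provide. Section 11.0 plans baseline-adjusted mixed models for the secondary outcomes too.

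**Working it through.** **Inputs from the protocol (Sections 6.0, 8.0 and 11.0).** Planned n = 30; attrition: "we conservatively incorporated a 10% attrition rate in our power calculation"; 30 × 0.9 = 27 evaluable. Target: "Our sample size has 80% power to detect an effect size of 0.8 standardized mean difference in the immune response". Alpha 0.05, taken as two-sided. Sequences AB and BA, taken as 1:1. Visits 2 to 5 fall at about weeks 0, 5, 9 and 14. **Assumed:** all correlations, and equal variances at the four visits. Vitamin D and demographic covariates are left out.

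**1. The plan's own figure.** Take 0.8 in within-woman SD units. The standard error of the contrast is √(2/27) = 0.272, the noncentrality is 0.8/0.272 = 2.94, and with 25 degrees of freedom power is 80.6%. The stated 80% is reproduced, with no credit taken for baseline adjustment.

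**2. The two slopes.** Let b be baseline and y the end-of-period value.
- Within slope: w = Cov(y₁−y₂, b₁−b₂) / Var(b₁−b₂).
- Between slope: Cov(y₁+y₂, b₁+b₂) / Var(b₁+b₂).

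With equal correlation ρ among all four visits, w = 0 and the between slope is 2ρ/(1+ρ). At ρ = 0.7 this is 1.4/1.7 = 0.82.

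**3. Variance of the contrast.** If the model uses slope k, the variance relative to no baseline is about 1 + k² − 2kw. The split form uses k = w and gives about 1 − w². The ratio of single to split is therefore about 1 + (k−w)²/(1−w²), before the small cost of estimating w. At ρ = 0.7 the fitted single slope averages k = 0.65, so the ratio is about 1 + 0.65² = 1.42.

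**4. Simulation.** REML random-intercept fits, n = 27, 1,200 trials per row. Decaying correlation is a constant participant part plus a remainder that shrinks by the stated factor per week.

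| Assumed correlation | w | Between | Fitted k | Variance, single/split | Variance, single/none |
|---|---|---|---|---|---|
| Equal, 0 | 0.00 | 0.00 | −0.01 | 0.97 | 1.03 |
| Equal, 0.3 | 0.00 | 0.46 | 0.25 | 1.06 | 1.10 |
| Equal, 0.5 | 0.00 | 0.67 | 0.43 | 1.18 | 1.23 |
| Equal, 0.7 | 0.00 | 0.82 | 0.65 | 1.41 | 1.46 |
| Equal, 0.8 | 0.00 | 0.89 | 0.77 | 1.57 | 1.62 |
| Decaying, part 0, factor 0.9 | 0.24 | 0.74 | 0.57 | 1.10 | 1.08 |
| Decaying, part 0.7, factor 0.9 | 0.24 | 0.94 | 0.87 | 1.39 | 1.36 |
| Across periods 0.7, within 0.8 | 0.33 | 0.88 | 0.78 | 1.20 | 1.13 |
| Across 0.5, within 0.8 | 0.60 | 0.87 | 0.79 | 1.03 | 0.72 |
| Across 0.3, within 0.8 | 0.71 | 0.85 | 0.79 | 0.99 | 0.53 |

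Further simulation sets of 600 to 1,500 trials per setting put the single/split excess at 12-18% for equal correlation 0.5, 30-41% for 0.7 and 50-68% for 0.8. The treatment estimate was unbiased in every model, and Type I error was about 5% either way.

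**5. Power, if 0.8 is in within-woman SD units.** Single slope against split: 76% and 78% at equal correlation 0.3; 72% and 77% at 0.5; 65% and 77% at 0.7.

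**6. Carry-over.** Let dried plum taken first leave λ at Visit 4.
- If λ persists in full to Visit 5, the bias is −(1−k)λ/2. With an assumed λ = 0.4 SD and ρ = 0.7, the single slope gives −0.35 × 0.2 = −0.07 and the split (k = 0) gives −0.20. Simulated root mean square errors are 0.196 and 0.254.
- If λ is gone by Visit 5, the bias is +kλ/2. The single slope gives 0.65 × 0.2 = 0.13 (0.12 in simulation) and the split about 0. Simulated root mean square errors are 0.216 and 0.158.

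**The case against.** The strongest reply is that the protocol does not fix the specification. A reader might infer from Section 11.0 that the trial is committed to a single period-baseline slope. The text names baseline measures only, and Section 6.0 also uses the word baseline for the data collected at Visit 2. A Visit 2 covariate is constant within woman and costs the within-woman contrast nothing. How a covariate is parameterised is often left to the SAP, which is not at hand. This stands as a limit on the wording. It does not remove the point, because blood at each period's start, an end-of-period response and the carry-over argument all point to period baselines, and the model as written shows no split.

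A reader might also infer that the trial falls short of 80% power. The documents do not support that, because Section 11.0 does not say which SD the 0.8 is measured in. In total-SD units, power without baseline is 97.9% at correlation 0.5 and 99.9% at 0.7. Inflating the variance by 1.23 and 1.46 still leaves about 95% and 99%.

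A third inference, that the primary result would be biased or the test invalid, is not supported either: without carry-over neither happens.

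Nor is the split always at least as precise. At zero correlation the single slope has a variance ratio of 0.97. Where visits within a period are much more alike, the single covariate does well: at across 0.5 and within 0.8 it cuts variance by 28% against no baseline.

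Finally, the single slope partly offsets carry-over that lasts undiminished to Visit 5, and the split offsets less. That is a real trade-off, but it reverses if the carry-over has gone by Visit 5.

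**Conclusion.** The point holds as a conditional loss of efficiency on the natural reading of Section 11.0. The size depends on correlations that the protocol does not give:
- about 0-10% extra variance when visits within a period are clearly more alike than visits across periods, and up to about 20% where the gap is only 0.1;
- about 10-40% under decaying correlation;
- about 12-18%, 30-41% and 50-68% at equal correlation 0.5, 0.7 and 0.8, where the single slope can be less precise than leaving baseline out.

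The figures rest on 27 evaluable women, 1:1 sequences, equal variances and no carry-over. The loss bears on the 80% target only if the 0.8 is in within-woman SD units. The change is still worth making: at zero correlation the split gives up about 3% of variance, while the single slope can give up 30% or more at correlations that are plausible for stable markers.

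**What to change.** In Section 11.0, state that the period baselines (Visits 2 and 4) are used. For each outcome, replace the baseline term by two: the woman's mean of her Visit 2 and Visit 4 values, and the period's deviation from that mean. Keep treatment, period and the random participant effect. If outcomes are log-transformed, form both terms on the log scale.

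The change takes one sentence and no new data, and is best made before outcome data are seen. It uses one extra degree of freedom and costs up to about 3% more variance if the visits are uncorrelated. It offsets less of any carry-over that persists undiminished to Visit 5, but gives less bias if carry-over is present at Visit 4 and gone by Visit 5.

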**Objective 2.** Assess the changes in the gut microbiota and gut-derived metabolites in response to dried plum compared to the control in stool and serum samples collected pre- and post each treatment arm. *Stool and serum samples will be collected and the change in gut microbiota taxa and fecal and serum metabolites in response to dried plum will be determined.*

**Objective 3.** Determine whether: a) serum vitamin D influences the immune, metabolite and microbiota response to dried plum; and b) the relationship of the immune, metabolite and microbiota outcomes to the bone resorption marker, c-terminal telopeptide 1 (CTX-1) and bone formation markers such as procollagen type 1 N-terminal peptide (PINP). *Serum 25(OH)vitamin*

*D and bone biomarkers (e.g., CTX-1 and PINP) will be assessed and their relationship to outcomes from Objective 1 & 2 will be explored.*

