### **3.0 OUTCOME MEASURES AND ENDPOINTS:**

The **primary outcomes** of this study will be change in circulating Th17 cells and their function in *ex vivo* experiments, and inflammatory cytokines (e.g., IL-6 & IL-17).

**Secondary outcomes** will include alterations in circulating Treg cells, their function and Th17/Treg ratio, other immune cells that affect T cells (e.g., B regulatory cells and natural killer cells), serum and fecal metabolites, microbiota taxa, and serum 25(OH)D, cytokines (e.g., TNF- $\alpha$  & IL-10), and the bone resorption and formation markers (e.g., CTX-1 and P1NP).

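### A single alpha of 0.05 for every analysis leaves the share of false findings uncontrolled if taxa and metabolites are tested one by one

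*Protocol*

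**What the plan says.** Objective 2 in Section 2.0 is to "Assess the changes in the gut microbiota and gut-derived metabolites in response to dried plum compared to the control". Its method statement adds that "the change in gut microbiota taxa and fecal and serum metabolites in response to dried plum will be determined". Section 3.0 lists "serum and fecal metabolites, microbiota taxa" among the secondary outcomes, and Section 8.0 stores serum "for metabolomics, cytokines, 25(OH)D and bone biomarkers".

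Section 11.0 gives the analysis: "for secondary outcome measures (i.e., gut microbiota, metabolites, and bone resorption markers), we will use separate mixed effects models", adjusted for baseline, period and demographic covariates. It later plans to integrate "metabolomics, microbial taxa and bone biomarker data" with the T cell results by regression and to run a mediation analysis. It closes with "For all statistical analyses, alpha will be set at 0.05".

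The protocol mentions no false discovery rate, family-wise or other multiplicity procedure and gives no number of taxa or metabolites. Within Section 11.0 only the mediation analysis is called exploratory; Section 2.0 says that the Objective 3 relationships will be explored. The taxa and metabolite models carry no such label.

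**The concern.** A sentence that sets one alpha for every analysis is a stated rule, not a gap left for later. Applied to one model per taxon and per metabolite, it lets each non-responding feature through with probability 0.05. The share of false entries among the features called changed then depends on how many features truly respond, which nobody knows beforehand.

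What is at stake is the answer to Objective 2: which taxa and metabolites change with dried plum. Chance findings could also carry forward into the regression and mediation work.

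**Working it through.** **Inputs from the protocol.** Alpha is 0.05 (Section 11.0; two-sided assumed, since sidedness is not stated). The sample is 30 women in a crossover with 10% attrition, so 30 × 0.9 = 27 completers. The power statement reads "Our sample size has 80% power to detect an effect size of 0.8 standardized mean difference in the immune response".

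**Assumed, because the protocol gives no figure.** The number of features m (50 or 200), the share p that truly respond (0% to 50%), the power per responding feature, and the within-woman correlation r between periods.

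**1. The protocol's own power figure.** For a paired t-test, the effect in SDs of the within-woman difference is d_z = 0.8 / √(2(1 − r)), with 27 women:

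| r | d_z | power |
|---|---|---|
| 0 | 0.566 | 0.81 |
| 0.25 | 0.653 | 0.90 |
| 0.5 | 0.800 | 0.98 |

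The stated 80% is reproduced at r = 0. It covers the immune response only, so using 80% for taxa and metabolites is itself an assumption.

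**2. No feature responds.** Expected false positives are m × 0.05: 2.5 for 50 features and 10 for 200. With independent features, the chance of at least one is 1 − 0.95^50 = 92% for 50 and above 99.9% for 200.

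**3. Some features respond.** The expected false share among features called changed is

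0.05(1 − p) / [0.05(1 − p) + power × p].

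For example, with p = 0.10 and power 0.80: 0.045 / (0.045 + 0.080) = 0.36.

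| Power | p = 5% | p = 10% | p = 20% | p = 50% |
|---|---|---|---|---|
| 0.30 | 76% | 60% | 40% | 14% |
| 0.50 | 66% | 47% | 29% | 9% |
| 0.80 | 54% | 36% | 20% | 6% |
| 0.979 | 49% | 31% | 17% | 5% |

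The number of features cancels out of this ratio, so the false share does not depend on m.

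**4. Effect of Benjamini-Hochberg at 5%.** Simulation with 200 independent features, 27 women and 1,500 runs; mean false share, unadjusted 0.05 against Benjamini-Hochberg:

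| p | d_z 0.8 | d_z 0.566 |
|---|---|---|
| 5% | 48% vs 4.8% | 53% vs 5.0% |
| 10% | 31% vs 4.3% | 35% vs 4.2% |
| 20% | 17% vs 4.1% | 20% vs 3.8% |
| 50% | 5% vs 2.6% | 6% vs 2.4% |

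For independent features the theoretical value under Benjamini-Hochberg is 0.05(1 − p): 4.75%, 4.5%, 4.0% and 2.5%. The simulation agrees. With no responders, at least one feature passes in essentially every run unadjusted and in about 5% of runs after adjustment. With features correlated at 0.5 in blocks of 20 and 10% responding, the false share is 30% vs 4.7% (d_z 0.8) and 34% vs 4.3% (d_z 0.566).

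**5. Price in detections.** With 10% of 200 features responding (20 true responders), mean detections fall from 19.6 to 16.7 at d_z 0.8 and from 16.2 to 6.6 at d_z 0.566.

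**The case against.** The strongest objection is that feature-level multiplicity is normally settled in a statistical analysis plan, which may exist and is not at hand. A plan that compared adjusted p-values with 0.05 would not contradict the protocol. That is possible, and the proposed sentence would then simply confirm it. But the protocol does not leave the level open: it fixes 0.05 for everything without exception, and a reader would ordinarily apply that to the p-value of each model.

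Second, feature-by-feature testing is inferred. The separate models follow a list of three outcome classes, and the background's example of gut-derived metabolites is short chain fatty acids, which could be a small panel. If only a few summary measures are tested, the concern largely falls away. Against that, the protocol speaks repeatedly of taxa and of metabolomics and names no diversity index or other summary measure.

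Third, the figures describe a general property of unadjusted testing, not a measured defect of this trial, and the simulation uses paired t-tests instead of the planned covariate-adjusted mixed models. That stands, which is why ranges are shown. The 100% figure with no responders is also true by definition: any feature that passes Benjamini-Hochberg in that case is false too. The gain there is that this happens in about 5% of trials instead of nearly all.

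Finally, with about 27 completers the loss of detections is real, and labelling all feature-level results exploratory would be a defensible alternative.

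**Conclusion.** The concern holds, conditional on feature-level testing. Under the rule as written, the false share among taxa and metabolites reported as changed can lie anywhere from about 5% to 100%, depending on a response rate the protocol does not give. Benjamini-Hochberg at 5% holds the average at about 2% to 5% wherever there are true responders. If half the features respond, the gain is small, from 5–6% to 2–3%.

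The finding rests on assumed response shares, assumed power per feature and the reading of separate models as one per feature. It touches secondary and exploratory results only, and the protocol promises no formal list of responders. It should be changed, but it does not threaten the trial's main conclusion. Confidence is moderate because the feature-level reading is inferred.

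**What to change.** Restrict the closing alpha sentence in Section 11.0. For feature-level tests of microbial taxa, fecal metabolites and serum metabolites, state that the 0.05 applies to Benjamini-Hochberg adjusted p-values within each of these three families, and that unadjusted p-values are also reported and labelled exploratory.

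This takes one or two sentences and standard software. Visits, samples and the primary analysis do not change. The price is the lower detection rate shown above; reporting the unadjusted p-values keeps the weaker signals visible.
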